Study Abstract: Quell is a class II medical device with FDA 510(k) clearance for the symptomatic relief and management of chronic intractable pain, without a prescription. It operates by using an electrical stimulator to activate peripheral sensory nerves and trigger analgesia. This device has great potential for significantly decreasing opioid use in patients

who have chronic pain secondary to serious illnesses and thus improve their quality of life, but has not yet been tested for cancer related pain. This study investigates the utility of the device in improving pain in patients with cancer while decreasing their overall opioid consumption.

Hypothesis: We hypothesize that Quell and its associated mobile application will decrease the overall opioid consumption of our test population while providing pain relief as self-reported by the study participants.

Purpose of the Study Protocol: To study effects Quell has on opioid consumption and pain relief in patients with cancer.

Rational: The prevalence of pain is high in patients with advanced chronic illness such as cancer. Despite increasing interest in, and efforts to improve its management, pain remains poorly controlled in nearly half of all patients with cancer, with little change in the past 20 years. (1). The prevalence of cancer-related pain has ranged from 14% to 100% depending on what surveys are evaluated, (2) and the incidence of pain has been shown to be similar across stages of disease. (3). Further, it has been shown that previously healthy people can be severely debilitated with poor quality of life during or even after curative treatments leave them with continued pain (4,5). Opioids are the mainstay of the medical management of moderate to severe pain and are used, in addition to appropriate adjuvants, by oncologists and palliative medicine physicians to help manage cancer related pain. However, given the associated side effects and the stigma of opioids both on the part of the patient's pain. Neuropathic pain in particular, is a challenge because while opioids and their adjuvants do help, there is no clear consistent medication that is proven effective above the rest (6).

Quell is a novel Wearable Intensive Nerve Stimulation (WINS) device that has FDA clearance for treatment of chronic pain continuously, including during sleep. Its mechanism of action is based on Transcutaneous Electrical Nerve Stimulation (TENS). It utilizes a precise high power electrical stimulator to activate peripheral sensory nerves and trigger analgesia. Though this device has efficacy for chronic and neuropathic pain (7), it has yet to be tested in this highly needed patient population, and has immense potential to significantly improve their quality of life.

2. Study Background

In 2015, 14.5 million Americans were living with a recent or remote history of cancer. (8,9). Pain is among the most, if not the most distressing sequelae of cancer and its associated treatments, and remains poorly managed worldwide. The devastation of living with uncontrolled pain has a significant effect on quality of life, physical functioning, and psychological distress.

Cancer related pain develops from complex interactions among cancer cells, the immune system, and the peripheral and central nervous systems (10,11). Cancer cells and the local immune cells produce a wide range of substances that stimulate the pain receptors. Once pain receptors are stimulated, impulses are transmitted first by afferent A δ fibers and then by separate slower C fibers. These fibers end in cell bodies in the dorsal root or trigeminal ganglion, which then interact with neurons in the central nervous system cells in the spinal cord. These cells synapse to the contralateral thalamus from which impulses are transmitted to regions of the cortex via somatosensory pathways. Visceral pain arising from nociceptors in internal organs is mostly transmitted by C fibers. It is often less well localized and less sharp than somatic pain, and is triggered by direct irritation from the tumor, distention.

The subjective nature of cancer pain derives in part from the perception of pain. The perception of pain is known to vary depending on factors such as anxiety, depression, distraction, etc. These factors have no direct relationship to the pain receptors, or the painful stimulus caused by the interplay between the cancer cells and immune cells. However, the fact that these factors impact the pain overall, indicates the presence of additional mechanisms that alter pain transduction and perception (12). One mechanism is the descending inhibition from midbrain and higher regions that contain high concentration of opioid receptors. Various neurotransmitters are involved in mediating this pain inhibition pathway including GABA and serotonin, but most important are the endogenous opioids, explaining why synthetic opioids work so well to inhibit pain (13).

The pain gate theory states that activation of sensory nerves (A β fibers) closes a "pain gate" in the spinal cord that inhibits the transmission of pain signals carried by nociceptive afferents (C and A δ fibers) to the brain (14). Although it is activated by localized peripheral nerve stimulation, the descending pain inhibition system has analgesic effects that may extend beyond the stimulation site to provide broad pain relief (15-19).

High frequency nerve stimulation, such as with a WINS device, induces an elevation in enkephalins that act through the δ -opioid receptor (20,21). Synthetic opioids mostly act through μ and κ -opioid receptors. All three of these receptors are involved in descending pain inhibition.

Clinical researchers have reported good clinical success with cutaneous electrical stimulation using 16 different electrical currents, assembled into packages, and transmitted to the existing nerves using modified electrocardiogram pads for 30 minutes a day (22,23).

TENS is characterized by a number of electrical parameters including the stimulation pulse shape, amplitude, duration, pattern, and frequency (24). Although all the parameters can be adjusted in an attempt to achieve maximal analgesia, only pulse intensity (24,25-27) has a clear influence. Stimulation at an intensity below the level of sensory perception does not provide pain relief, and the degree of analgesia is correlated to the stimulation intensity (28).

Quell is a wearable, automated electrical nerve stimulator designed for people with pain, that includes technology to provide convenience while optimizing pain relief. It consists of four components: a therapy pod, an electrode array, a band, and a mobile app. The therapy

pod, which contains the electronics, is placed in the band and then an electrode array is attached by snapping it to the therapy pod. The electrode array consists of 4 hydrogel pads that provide a large (60 cm2) interface between the stimulator and the patient's sensory nerves. The hydrogel typically lasts 2 weeks or 100 hours of use, and is formulated to reduce skin irritation. The band is placed on the upper calf where therapy is initiated by pressing the button. The reason for placement on the upper calf is that this area has a high density of cutaneous sensory innervation that enables robust stimulation of A β fibers. When placed on the upper calf, the electrode array is circumferential and will stimulate sensory dermatomes S2- L4 providing a broad neural input to trigger analgesia through the descending pain inhibition system.

A calibration procedure is used to estimate the optimal therapeutic stimulation intensity (within the recommended range) for each patient. This is accomplished by an algorithm that automatically determines an intensity within the recommended therapeutic range that is appropriate for the patient. Once calibrated, all subsequent therapy is automatically delivered at the required intensity. The patient has the option of manually adjusting intensity at any time and the device incorporates these changes in subsequent therapy sessions. Quell automatically compensates for nerve desensitization by adaptively increasing the intensity over the course of the one-hour therapy session. The device enables long- term unattended therapy, such as overnight, by automatically restarting hour-long therapy sessions every other hour as long as the device remains on the leg. It also monitors the amount of time it is on the same region of skin and alerts the patient to ventilate the area to reduce the risk of irritation. Finally, Quell has embedded intelligence to determine if the patient is sleeping and automatically reduces the intensity to provide overnight pain relief without disturbing sleep.

The therapy pod is powered by a Lithium-Ion battery that provides 30-40 hours of therapy (4-7 days of typical use) if fully charged. The battery can be recharged in 2-3 hours by plugging the device into an AC adapter.

3. Study Design

The study is a single site, double blinded, placebo controlled randomized clinical trial. 40 subjects will be selected based on the inclusion criteria stated below and then randomized to either the intervention group or the placebo control group. Prior to the start of this study, a Controlled Substance Utilization Review and Evaluation (CURES) reports will be acquired to establish baseline number of opioid prescriptions for each subject. Subjects will track how consistently they are using pain medications, both opioids and non-opioids, during the two weeks prior to the start of the study. They will also provide twice daily recordings of their pain intensity via a mobile application. At the end of this two-week period, each subject will be fitted with a Quell or a sham device, including initial calibration to the subject's comfort level as described in the background section.

The sham device is identical to Quell in all aspects with one exception. While Quell delivers 1 hour of continuous stimulation during a therapy session, the sham device delivers three 2-minute periods of stimulation at 0, 28 and 58 minutes within the therapeutic session. This limited stimulation should have little to no analgesic effect but should suggest to the subject that they are receiving therapy.

Neither the principal investigator, nor the co-investigator or the subject will know if they are given a sham device or the actual Quell device. The study coordinators will be the only ones who will be aware of which intervention subjects receive. At the end of the study, subjects will be asked if they thought they had the sham or actual device. Both the principal and the co-investigator will be asked to identify which subjects they thought had Quell vs the sham device, prior to analysis of the data.

Once the study subjects have started using the device, we will also be able to monitor and track their sleep wirelessly via the mobile application as long as they are wearing the device. Subjects will receive weekly check in's to monitor the functionality of the device and to help troubleshoot any issues with the device for the duration of subject participation in the study. These check-ins will take place in person, by phone, and or per subject's usual outpatient oncology visits. Each subject will use their device for 8 weeks, during which they will continue to track their pain, sleep and frequency of pain medication use as stated above. Study investigators will receive automated alerts via email to ensure that study are participants using their devices and that the devices are powered on at regular intervals for the duration of the study.

Both Quell and the sham device communicate via Bluetooth with the same mobile application. This application provides the subjects with a dashboard of device information, trending data on device usage, and sleep quality. This same information will be synced to a cloud so that investigators involved in the study can collect this data remotely, as well as monitor adherence with the device.

Total duration of subject participation will be 10 weeks.

4. Criteria for Evaluation

Primary Efficacy Endpoint

The primary endpoint is a reduction in daily opioid use assessed at weeks 2, 4, 6, 8 and 10 of the study as recorded by the subject in their analgesia diary. This diary will be a preformatted paper form given to each subject at the start of the study, and will include the name and dosage of all the analgesic pain medications prescribed to the subject, as well as any over the counter pain medications the subject will be using. The subjects will be asked to log what times they take their pain medication each day. This diary will then be reviewed and logged into our secure database at each of the clinic visits as stated above. Per previous studies with a similar design, a 20-30% change in opioid consumption is clinically relevant. This end point is chosen as the overall goal of this study is to provide a novel way for patients with cancer to have optimal pain control while reducing their overall opioid use.

Secondary Endpoints

Change in pain intensity via the mobile app and as described by the subject using the Shortform McGill Pain Questionnaire-2 SF-MPQ-2 and the Patient Global Impression of Change (PGIC). The pain intensity scores will be measured twice daily using the mobile application and the SF-MPQ-2 will be completed during weeks 0,2,4,6 and 10 of the study. The PGIC will come completed at week 10.

These tools were chosen because a treatment should demonstrate a statistically and a clinically significant effect. Well-researched cutoff method suggests, that a 30% reduction of pain can be considered clinically significant (29). This level corresponds with a 2 points on a 0 to 10 pain intensity numerical rating scale (30). The Short-form McGill Pain Questionnaire (SF-MPQ-2) assesses the major symptoms of both neuropathic and nociceptive pain and can be used in studies of epidemiology, natural history, pathophysiologic mechanisms, and treatment response. Numerous studies have demonstrated its reliability, validity, and responsiveness in diverse samples of subjects with acute and chronic pain. Subjects rate their pain in sensory and affective terms and use a visual analog scale. The self-report measure Patient Global Impression of Change reflects a subject's belief about the efficacy of treatment. It is well studied and widely used in chronic pain clinical trials. PGIC is a 7-point scale depicting a subject's rating of overall improvement of a treatment intervention. Subjects rate their change as "very much improved," "much improved," "minimally improved," "no change," "minimally worse," "much worse," or "very much worse."

Changes in quality of life as measured by the Functional Assessment of Cancer The EORTC Quality of Life C-15- PAL measurement scale assessed at time of enrollment (week 0) week 6 and week 10 of the study. This is a validated questionnaire developed to assess the quality of life of palliative care cancer subjects.

Additional analysis includes changes in objective sleep measures using the mobile application and also The Sleep Scale developed for the Medical Outcomes Study. We will also look at the other characteristics of the pain that are automatically monitored with Quell/Sham device and its mobile application such as activity level.

5. Subject Selection

Study Population

40 Subjects with a diagnosis of metastatic cancer of any type, with cancer related pain on active chemotherapy treatment, who meet the inclusion and exclusion criteria will be selected for participation in this study

General Inclusion Criteria:

- 1. Male or Female greater than or equal to 18 year of age at visit one.
- 2. Documented diagnosis of metastatic cancer, who has cancer/chemotherapy related pain, with a prognosis of 6 month or greater as determined by the primary oncologist.

- 3. Visual evidence that subject owns a smart phone and is able to use basic mobile applications such as downloading an app, opening the app, and performing one simple task within the app.
- 4. Subject speaks and reads English fluently.
- 5. Subject able to understand and grant informed consent.
- 6. Live in an area with cellular data connectivity available as provided by the subject.
- 7. Documented adherence with clinic follow up visits per medical records.
- 8. Subject using at least one opioid medication on a daily basis.

Exclusion Criteria:

- 1. Subject has a cardiac pacemaker, implanted defibrillator or other implanted electronic device.
- 2. Inability to complete subjective data as required; e.g. on mobile application and questionnaires.
- 3. Does not live in an area with suitable cellular data connectivity.
- 4. Has infrequent scheduled clinic visits.

Subject Recruitment

Subjects will be recruited from the Scripps Mercy Oncology Clinic, San Diego California.

6. Concurrent Medications

All subjects should be maintained on their same oncology treatment protocol as directed by the primary oncologists during the study as they were prior to the onset of the study. Any changes in medication type, doses and frequency should be discussed with the treating physician and documented.

7. Study Procedures

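### No eligibility criterion covers current or past use of Quell or another TENS device, so some subjects could record their baseline on active stimulation and prior Quell users could recognise the sham

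*Protocol*

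**What the plan says.** **Availability.** The protocol's Study Abstract describes a device with "FDA 510(k) clearance for the symptomatic relief and management of chronic intractable pain, without a prescription". The rationale that follows says it works on the TENS principle.

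**Eligibility (protocol Section 5).** There are eight inclusion and four exclusion criteria. The treatment-related inclusion is "Subject using at least one opioid medication on a daily basis". The only exclusion about a device is "Subject has a cardiac pacemaker, implanted defibrillator or other implanted electronic device". The other three concern inability to supply data, lack of cellular coverage and infrequent clinic visits.

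**Baseline (Section 3).** Subjects track analgesic use and pain "during the two weeks prior to the start of the study", and the study device is fitted at the end of that period. Nothing is said about a stimulator that the subject already owns.

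**Active and sham (Section 3).** The protocol states "While Quell delivers 1 hour of continuous stimulation during a therapy session", whereas "the sham device delivers three 2-minute periods of stimulation at 0, 28 and 58 minutes within the therapeutic session". At the end, subjects guess their allocation. The principal investigator and co-investigator also guess, before the data are analysed.

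**Other treatments.** Section 7.3.1 has concurrent therapies documented at screening and at each scheduled clinic visit. Section 11.3 counts use of a prohibited medication as a violation, but no list of prohibited treatments is given and a device is not a medication. The SAP (Section 2.5) does not name stimulator use among the baseline characteristics it compares or the confounders it adjusts for.

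**The concern.** The primary endpoint is reduction in daily opioid use, and the sample size is built on percent change. Both need a baseline that precedes the treatment under test. A candidate who already wears Quell or another TENS device and takes a daily opioid passes every criterion and completes the run-in on active stimulation. Three things can then happen:

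- Allocated Quell, the subject has little further change to show.
- Allocated sham and giving up the personal device, the subject loses active stimulation, and opioid use may rise.
- Allocated sham and keeping the personal device, the subject is actively stimulated throughout.

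In none of these does the comparison measure what happens when a patient starts Quell. The trial would mix starting the device with continuing or stopping it. The SAP's adjustment for baseline opioid dose does not repair this, because a dose does not show whether stimulation has already lowered it.

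The second issue is blinding. Someone who has used Quell knows that a session is continuous, and may notice long silent stretches. The primary diary and the pain, PGIC and quality-of-life outcomes are self-reported, so a subject's belief about allocation can affect them.

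**Working it through.** **1. Is the gap closed elsewhere?** Section 5 has no relevant criterion. Section 6 deals with oncology treatment and medication changes. Section 7.3.1 records concurrent therapies but excludes no one. The Section 8 checklists that carry the item (Visits 1, 3, 4 and 6) name concomitant medications only, and Visit 2, when the device is issued, has no such item. The gap remains.

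**2. Sham exposure.** 3 × 2 = 6 minutes of 60, or 10% of the active session.

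**3. The plan's own power.** Inputs from protocol Section 10: 20 per arm, difference 20 percentage points, SD 22 or 19, two-sided two-sample t-test, alpha 0.05. Power comes from the noncentral t with 38 degrees of freedom and noncentrality d / (SD × √(2/20)).

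- SD 22: 20 / (22 × 0.3162) = 2.87, power 80.0%.
- SD 19: 20 / (19 × 0.3162) = 3.33, power 90.0%.

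Both protocol figures reproduce. (The SAP pairs 90% with SD 22 and 80% with SD 19. The calculation supports the protocol's pairing. That is a separate matter.)

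**4. One-sided illustration.** The number of users is not given, so k is an assumption. Suppose k Quell-arm subjects are already at full benefit and show no change, no sham-arm subject is affected, and the SD is unchanged. The difference becomes 20 × (1 − k/20) = 20 − k.

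| k in Quell arm | Difference | Power, SD 22 | Power, SD 19 |
|---|---|---|---|
| 0 | 20 | 80.0% | 90.0% |
| 1 | 19 | 75.9% | 86.9% |
| 2 | 18 | 71.3% | 83.1% |
| 4 | 16 | 61.1% | 73.7% |

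**5. Users in both arms who give up their own device.** Assume a full benefit of 20% and a planned sham change of zero (the documents state only the difference). A Quell-arm user shows 0. A sham-arm user goes from 80 to 100, which is +25%. With k such users in each arm:

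- Quell-arm mean: −20 × (20 − k)/20 = −(20 − k).
- Sham-arm mean: 25k/20 = 1.25k.
- Difference: 20 − k + 1.25k = 20 + 0.25k, so 21 at k = 4.

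The mean difference hardly moves, although part of it now comes from withdrawing stimulation.

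**6. Users only in the sham arm who give up their device.** The difference is 20 + 1.25k, so 25 at k = 4, an inflated contrast.

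**7. Sham-arm users who keep their device throughout.** They show about zero change. If the planned sham change is zero, they cost nothing, and any dilution comes from the Quell arm alone.

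**The case against.** The strongest reply is that the harm is hypothetical and its size unknown. The protocol calls the device novel and untested in cancer pain, and nothing shows that any candidate at this single clinic uses one. Four users in the Quell arm would imply roughly eight among 40, or 20% of enrolment, which the documents do not support. Randomisation spreads users over both arms, and step 5 shows that the effects can then nearly offset. This stands. A reader might infer from the table that the trial should expect that loss of power; the documents do not support this, because it is one scenario in one direction.

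Three other inferences also go too far. The run-in is nowhere described as an untreated reference: every subject takes a daily opioid, so it is a usual-care baseline. Outcomes are not all self-reported: app sleep and activity data and the CURES prescription reports are not. And an exclusion at entry would not stop a sham subject from acquiring a device mid-study.

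The existing safeguards count for something. Section 7.3.1 makes current stimulator use recordable, and the allocation guesses can reveal unblinding. But both work after the fact: they neither keep a current user out nor prevent recognition of the sham. A naive subject might also notice the 6-in-60-minute pattern, so the added effect of past Quell use is plausible rather than shown. Offsetting means do not answer the main point either, since a contrast partly made of withdrawal effects is not the effect of starting Quell.

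**Conclusion.** The gap is real. As written, the criteria admit current and past users of the test device and of similar devices. For current users the contrast does not estimate the effect of starting Quell, and past Quell users may recognise the sham.

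The size cannot be fixed from the documents, which give no prevalence. The bias can dilute the contrast, inflate it, or largely cancel between arms. The power falls in step 4 (to 76%, 71% or 61% at SD 22; to 87%, 83% or 74% at SD 19) hold only for one, two or four affected Quell-arm subjects, full prior benefit, no affected sham-arm subjects and an unchanged SD. They show that with 20 per arm a few such subjects could matter. They are not a forecast. Nor do the documents support saying that users will enrol or that blinding will fail. No figure in the protocol's sample-size statement is wrong because of this gap.

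**What to change.** 1. Add one exclusion criterion in protocol Section 5: any previous use of Quell, and use of any TENS or similar electrical nerve stimulation device during the run-in or within a period before it that the sponsor specifies. The Quell part protects the blind, and the run-in part protects the baseline.

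2. Add one yes/no item on non-study stimulator use to the concurrent-therapy record at every visit, including Visit 2, and report it by arm. This captures contamination during the trial, which the exclusion cannot prevent.

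The planned 20 per arm and the stated 80% and 90% power are unchanged. The cost is one line of eligibility text, one case report form item and the loss of a few otherwise eligible candidates. If prior use is rare, almost nobody is lost; if it is common, the exclusion matters more.
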